# NON-INTERVENTIONAL STUDY PROTOCOL

# **Study Information**

Title	Predictors of Treatment and the Comparative Clinical and Economic Outcomes among Non-Valvular Atrial Fibrillation Patients Treated versus Untreated with Oral Anticoagulant Therapy
Protocol number	B0661142
Protocol version identifier	1.0
Date of last version of protocol	13 June 2019
EU Post Authorization Study (PAS) Register Number	
Medicinal Product	Apixaban
Research question and objectives	Primary Objective: 1. Estimate patients ever-treated and never-treated with oral anticoagulants (OACs) and the predictors of OAC treatment among elderly Medicare non-valvular atrial fibrillation (NVAF) population.
	Secondary Objectives:
	1. Analyze high-risk patient subgroups, such as CHA 2 DS 2 -VASc score and age subgroups, for the primary objectives.
	2. Compare the risk of major bleeding and major bleeding-related costs among elderly patients treated versus untreated with OACs in the Medicare NVAF population.
	3. Compare the risk of stroke/systemic embolism (SE) and stroke/SE-related costs among elderly patients

Do not distribute for purposes outside of specific activities related to development of FDAMAs114 compliant pieces. Content within this protocol is subject to change based on communication planning and input by external review committees.

# 1. LIST OF ABBREVIATIONS

Abbreviation	Definition
AE	Adverse Event
AF	Atrial Fibrillation
CAD	Coronary Artery Disease
CCI	Charlson Comorbidity Index
CHADS 2	Congestive heart failure, Hypertension, Age ≥75 years, Diabetes mellitus, Stroke
CHA 2 DS 2 - VASc	Congestive heart failure, Hypertension, Age ≥75 years, Diabetes mellitus, Stroke, Vascular disease, Age 65-74 years, Sex category
CHF	Congestive Heart Failure
CI	Confidence Interval
CMS	Centers for Medicare & Medicaid Service
СРІ	Consumer Price Index
DME	Durable Medical Equipment
DOACs	Direct Oral Anticoagulants
ER	Emergency Room
FFS	Fee-For-Service
HAS-BLED	Hypertension, Abnormal renal/liver function, Stroke, Bleeding history or predisposition, Labile international normalized ratios, Elderly, Drugs/alcohol

Do not distribute for purposes outside of specific activities related to development of FDAMAs114 compliant pieces. Content within this protocol is subject to change based on communication planning and input by external review committees.

#### Apixaban

NON-INTERVENTIONAL STUDY PROTOCOL

Abbreviation	Definition
HCPCS	Healthcare Common Procedure Coding System
ННА	Home Health Agency
HIPAA	Health Insurance Portability and Accountability Act
ICD-9-CM	International Classification of Diseases, Ninth Revision, Clinical Modification
ICD-10-CM	International Classification of Diseases, Tenth Revision, Clinical Modification
IPTW	Inverse Probability Treatment Weighting
MACE	Major Adverse Cardiac Events
NI	Non-Interventional
NVAF	Non-Valvular Atrial Fibrillation
OAC	Oral Anticoagulants
PAD	Peripheral Arterial Disease
PPPM	Per Person Per Month
RCT	Randomized Controlled Trial
SE	Systemic Embolism
SNF	Skilled Nursing Facility

Do not distribute for purposes outside of specific activities related to development of FDAMAs114 compliant pieces. Content within this protocol is subject to change based on communication planning and input by external review committees.

Apixaban NON-INTERVENTIONAL STUDY PROTOCOL

# **3. ABSTRACT**

**Title:** Predictors of Treatment and the Comparative Clinical and Economic Outcomes among Non-Valvular Atrial Fibrillation Patients Treated versus Untreated with Oral Anticoagulation Therapy

Version: 1.0

## Date of Protocol: May 31, 2019

**Rationale and Background:** Non-valvular atrial fibrillation (NVAF) patients have a substantial risk of ischemic stroke and systemic embolism (SE). Several direct oral anticoagulants (DOACs) have been approved in recent years; clinical trials have shown them to be similar to or better than warfarin regarding the risks of stroke/SE and major bleeding. Oral anticoagulant (OAC) prescription may be underutilized in AF patients at risk for stroke, and there are few data regarding OAC untreated NVAF patients in a real-world clinical setting. There is no recent evidence on untreated NVAF patients in a real-world clinical setting. In addition, the modifiable and unmodifiable factors associated with non-treatment are currently unknown. The burden of NVAF is expected to increase significantly over time, particularly hospitalization and health care costs. To develop effective strategies for reducing the overall disease burden, it is critical to understand the factors related to non-treatment in NVAF patients and the associated clinical and economic outcomes.

# **Objectives:**

# Primary

1. Estimate patients ever-treated and never-treated with OACs and the predictors of OAC treatment among elderly Medicare NVAF patients.

#### Secondary

- 1. Analyze high-risk patient subgroups (eg, CHA2DS2-VASc and age) for the primary objectives.
- 2. Compare the risk of major bleeding and major bleeding-related costs among elderly patients treated versus untreated with OACs in the Medicare NVAF population.
- 3. Compare the risk of stroke/SE and stroke/SE-related costs among elderly patients treated versus untreated with OACs in the Medicare NVAF population.

Do not distribute for purposes outside of specific activities related to development of FDAMAs114 compliant pieces. Content within this protocol is subject to change based on communication planning and input by external review committees.

#### Apixaban NON-INTERVENTIONAL STUDY PROTOCOL

- 4. Compare the risk of death among elderly patients treated versus untreated with OACs in the Medicare NVAF population.
- 5. Compare the all-cause health care costs among elderly patients treated versus untreated with OACs in the Medicare NVAF population.

**Study Design:** The study will be a longitudinal retrospective cohort analysis using the US Centers for Medicare & Medicaid Services (CMS) Medicare dataset from 01JAN2012-31DEC2016. The study will designate a 12-month baseline period prior to the identification period (01JAN2013-31DEC2016). This database only includes patients enrolled in fee-for-service (FFS) Medicare; those enrolled in managed-care plans will be excluded. Further, patient eligibility will be based on selection from the database according to the following inclusion and exclusion criteria (sections 2).

**Population:** Elderly patients (aged  $\geq 65$  years) will be required to have  $\geq 1$  inpatient or  $\geq 2$  outpatient medical claims (the 2 outpatient claims are  $\geq 7$  days apart) for AF during the identification period for the primary and secondary objectives. For the primary objective, two mutually-exclusive NVAF patient cohorts will be created: ever-treated with OAC and never-treated with OAC. For the secondary objective assessing clinical and healthcare utilization and costs, treatment status will be a time-varying covariate and ever-treated patients will contribute time-not-on-treatment to untreated effect.

For the primary and secondary objectives, the ever-treated with OAC population cohort will include newly diagnosed NVAF patients who ever initiated oral anticoagulant (OAC) treatment (apixaban, dabigatran, edoxaban, rivaroxaban, and warfarin) during the study period identified from 01JAN2013-31DEC2016. The never-treated with OAC population cohort will include newly diagnosed NVAF patients without any OAC claim from 01JAN2013-31DEC2016.

For the primary and secondary objectives, the first AF diagnosis date during the identification period will be used as the index date for both ever-treated and never-treated cohorts. Across both ever-treated and never-treated cohorts, all patients will be required to have a  $CHA_2DS_2$ -VASc $\geq 2$  and 12-months of continuous health plan enrollment, with medical and pharmacy benefits before the index date (baseline period). For the primary objective and high-risk subgroup analyses, patients will also be required to have 6-month continuous health plan enrollment, with medical and pharmacy benefits after the index date.

For the primary objective and high-risk subgroup analyses, the following patients will be excluded: an AF diagnosis any time prior to the first AF diagnosis; medical claims indicating a diagnosis or procedure for mitral valvular heart disease or heart valve replacement/transplant;

Do not distribute for purposes outside of specific activities related to development of FDAMAs114 compliant pieces. Content within this protocol is subject to change based on communication planning and input by external review committees.

Apixaban NON-INTERVENTIONAL STUDY PROTOCOL

or use of OACs during the baseline period. For the secondary objective assessing effectiveness, safety, and cost outcomes, patients will be further excluded if they had any of the following: venous thromboembolism; transient AF during the baseline period; pregnancy during the study period; hip/knee replacement surgery within 6 weeks pre-index date; or follow-up period = 0 day. In addition, among patients ever treated with an OAC, those with >1 OAC prescription claim at the index date will be excluded as well.

**Variables:** Baseline demographic and clinical characteristics will include age, gender, race, geographic region, Medicaid dual eligibility, Part-D low income subsidy, Charlson comorbidity index (CCI), CHADS2, CHA2DS2-VASc, HAS-BLED scores, prior bleeding/stroke events, congestive heart failure, diabetes, hypertension, chronic obstructive pulmonary disease, renal disease, myocardial infarction, dyspepsia or stomach discomfort, peripheral arterial disease, transient ischemic attack, coronary artery disease, history of falls, medication use, and index dose of DOAC. Baseline all-cause health care costs and utilization will be included.

For the primary objective and high-risk subgroup analyses, the following cohorts will be compared: a) ever-treated with OAC vs. never-treated with OAC; b) initiated with DOAC vs. never-treated with OAC cohorts; c) initiated with warfarin vs. never-treated with OAC; and d) initiated with DOACs vs. never-treated with OAC.

For the secondary objectives assessing effectiveness, safety, and costs outcomes, the following outcomes will be compared between cohort pairs (treated vs untreated, apixaban vs untreated, dabigatran vs untreated, rivaroxaban vs untreated, and warfarin vs untreated): time to stroke/SE, major bleeding, and death; medical costs related to stroke/SE and major bleeding; and all-cause health care costs and utilization.

**Data Sources:** The study will be conducted using Medicare Inpatient Data, Medicare Outpatient Data, the Medicare Carrier File, Medicare Part D Drug Events (PDE) Data, the Skilled Nursing Facility (SNF) File, the Home Health Agency (HHA) File, the Hospice File, the Durable Medical Equipment (DME) File, and the Medicare Denominator File.

**Data Analysis:** Means, medians, and standard deviations will be provided for continuous variables. Numbers and percentages will be provided for dichotomous and polychotomous variables. Bivariate comparisons of baseline characteristics and outcomes measures will be provided. Appropriate tests (eg, t-test, chi-square test) will be used, based on the distribution of the measure. Logistic regression models will be used to examine the predictors of treatment. For the secondary objectives assessing effectiveness, safety, and costs, the cumulative incidence rate for clinical outcomes (stroke/SE, major bleeding, and death) will be calculated. Inverse probability weighting (IPW) will be used to balance treatment cohorts. Cox regressions

Pfizer Confidential

Page 10 of 37

Do not distribute for purposes outside of specific activities related to development of FDAMAs114 compliant pieces. Content within this protocol is subject to change based on communication planning and input by external review committees.

Apixaban NON-INTERVENTIONAL STUDY PROTOCOL

with time-varying treatment status and marginal structural models (MSMs) will be used to compare the treatment effects, all-cause and stroke/SE and major bleeding-related health care costs. Data analysis will be executed using statistical software SAS version 9.4.

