## 8.2.1.2. Exclusion Criteria

- 1) Exclude patients with AF diagnosis prior to the index date;
- 2) Exclude patients with medical claims indicating diagnosis of mitral valvular heart disease or valve replacement procedure (see Appendix) during the 12 months prior to or on the index date;
- 3) Exclude patients who had a pharmacy claim for apixaban, dabigatran, edoxaban, rivaroxaban, or warfarin during the 12 months pre-index period.

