# 8.2.2. Secondary Objectives

## 8.2.2.2. Additional Exclusion Criteria

- 1) Exclude patients with medical claims indicating a diagnosis code for venous thromboembolism (VTE; see Appendix) during the 12 months prior to or on the index date;
- 2) Exclude patients with medical claims indicating a diagnosis or procedure code of transient AF (see Appendix) during the 12 months prior to or on the index date;
- 3) Exclude patients with medical claims indicating pregnancy (see Appendix) during the study period;
- 4) Exclude patients with medical claims indicating hip/knee replacement surgery within 6 weeks prior to the index date;
- 5) Exclude patients with 0 days of follow-up;
- 6) Exclude patients who initiated more than one OAC treatment on the index date.

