# 8.2.3. Cohorts

Patients eligible according to the above criteria will be assigned to the following cohorts:

Do not distribute for purposes outside of specific activities related to development of FDAMAs114 compliant pieces. Content within this protocol is subject to change based on communication planning and input by external review committees.

Apixaban NON-INTERVENTIONAL STUDY PROTOCOL

- 1) Ever-Treated Cohort: NVAF Patients had ≥1 pharmacy claim for apixaban, dabigatran, edoxaban, rivaroxaban, or warfarin from 01JAN2013-31DEC2016 on or after the first AF diagnosis
  - a. Apixaban cohort: Patients who initiated with apixaban on or after index date
  - b. Dabigatran cohort: Patients who initiated with dabigatran on or after index date
  - c. **Edoxaban cohort:** Patients who initiated with edoxaban on or after index date. Given the small sample size, edoxaban patients will not be included in the secondary clinical and healthcare utilization and costs analyses.
  - d. Rivaroxaban cohort: Patients who initiated with rivaroxaban on or after index date
  - e. Warfarin cohort: Patients who initiated with warfarin on or after index date
- 2) Never-Treated Cohort: NVAF patients with no pharmacy claim for an OAC from 01JAN2013-31DEC2016

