# 8.7. Data Analysis

When performing descriptive analysis of continuous data, means, medians, and standard deviations will be provided for continuous variables. When performing descriptive analysis of categorical data, numbers and percentages will be provided for dichotomous and polychotomous variables. Bivariate comparisons of baseline characteristics and outcomes measures will be provided. Appropriate tests (eg, t-test, chi-square test) will be used based on the distributions of the measures. The cumulative incidence rate for clinical outcomes (major bleeding, stroke/SE, and death) will be calculated. The incidence rate will be calculated as the number of patients who experience the event divided by the observed time at risk. An unadjusted Kaplan-Meier curve will be drawn to illustrate time-to-event. The sample size of each cohort will be evaluated before proceeding with multivariate analysis.

The secondary objectives are optional, depending on the sample sizes and results from the primary objectives. For example, given the potential differences between ever-treated and never-treated with OAC patients, should the predictors/confounders from the primary objective be considered profound for the comparisons between the cohorts, objectives 2-5 will not be conducted.

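### The primary analysis keeps patients with VTE, transient AF or recent hip/knee replacement, so some OAC use for other reasons counts as AF treatment and transient AF without OAC counts as untreated NVAF

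*Protocol*

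**What the plan says.** The protocol has two tiers of exclusions, and the Abstract and the body agree on them.

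- **Primary objective and high-risk subgroups (secondary objective 1).** Section 8.2.1.2 lists three exclusions. The first two are "Exclude patients with AF diagnosis prior to the index date" and "Exclude patients with medical claims indicating diagnosis of mitral valvular heart disease or valve replacement procedure". The third is an OAC pharmacy claim in the 12 months before index.
- **Secondary objectives 2-5.** For the effectiveness, safety and cost outcomes, the Abstract introduces the extra criteria with "patients will be further excluded if they had any of the following: venous thromboembolism; transient AF during the baseline period". Section 8.2.2.2 repeats them: item 1 begins "Exclude patients with medical claims indicating a diagnosis code for venous thromboembolism", item 2 covers transient AF, and item 4 covers hip/knee replacement in the 6 weeks before index.
- **Treatment status.** Section 8.2.3 makes a patient ever-treated on one claim for apixaban, dabigatran, "edoxaban, rivaroxaban, or warfarin from 01JAN2013-31DEC2016 on or after the first AF diagnosis". It sets no condition on why the drug was given. Never-treated means no OAC claim at all.

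The primary objective (Section 7) is to estimate the ever-treated and never-treated groups and the predictors of OAC treatment in elderly Medicare NVAF patients.

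**The concern.** In the primary analysis OAC treatment is the outcome. A claim written for another indication therefore affects the endpoint itself, not just a covariate. A patient with a VTE or joint replacement close to the AF index date, whose first OAC fill follows index, enters as treated NVAF. A patient with transient AF and no OAC claim enters as untreated NVAF.

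The background section presents the study as measuring untreated NVAF and explaining non-treatment. At stake are the reported treated share and the odds ratios. Both could partly reflect who had another reason for OAC, or who had AF that did not last. The protocol removes these groups from objectives 2-5, keeps them where treatment status is the endpoint, and gives no reason for the difference.

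**Working it through.** **1. Does anything else in the protocol compensate?**

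- Table 1 does not list VTE, transient AF or recent hip/knee replacement among the baseline variables.
- Section 8.7 uses stepwise selection, with the final covariates settled on clinical rationale and model fit. Adding the conditions is not barred, but it is not planned.
- Section 8.8 gives the primary objective only CHA2DS2-VASc and age subgroups.
- The limitations in Section 8.10 do not mention the issue.
- Primary exclusion 3 removes patients already on OAC in the year before index. What remains is VTE or surgery near index with the first OAC fill on or after index, plus earlier VTE with no OAC claim.
- Section 8.2.1.1 asks for two outpatient AF claims at least 7 days apart, which filters some transient AF. One inpatient claim still qualifies.

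**2. Effect on the treated share.** The plan states no figure to reproduce and gives no prevalences, so every input here is an assumption. Let p be the OAC share in NVAF without these conditions. For a group with cohort share g and OAC share q, the shift in the overall treated share is g × (q − p).

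VTE, with p = 50%:

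| VTE share | OAC share in VTE | Shift (points) |
|---|---|---|
| 1% | 80% | 0.01 × 0.30 = +0.3 |
| 2% | 90% | 0.02 × 0.40 = +0.8 |
| 3% | 80% | 0.03 × 0.30 = +0.9 |
| 6% | 90% | 0.06 × 0.40 = +2.4 |

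The 1-2% rows allow for the OAC-free requirement having already removed part of the group.

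Transient AF, with p = 50%:

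- Share 3%, 30% on OAC: 0.03 × (0.30 − 0.50) = −0.6 points.
- Share 10%, 10% on OAC: 0.10 × (0.10 − 0.50) = −4.0 points.

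A wider grid takes p = 40-60%, VTE or surgery in 0-10% with 80-95% on OAC, and transient AF in 0-10% with 10-30% on OAC. The extremes are 0.10 × (0.10 − 0.60) = −5.0 and 0.10 × (0.95 − 0.40) = +5.5 points. The two groups can partly cancel in the share, but both stay in the predictor model.

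**3. Effect on an odds ratio.** Take obesity, which Table 1 labels a potential predictor, and give it no true effect. Assume 20% obese, VTE twice as common in the obese, 85% of VTE patients on OAC and 50% of the rest. With overall VTE share v, the non-obese share is v / (0.8 + 0.2 × 2) = v / 1.2.

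- v = 3%: VTE in 2.5% of non-obese and 5% of obese. Treated shares are 0.5 + 0.025 × 0.35 = 0.50875 and 0.5 + 0.05 × 0.35 = 0.5175. OR = (0.5175/0.4825) / (0.50875/0.49125) = 1.036.
- v = 6%: treated shares 0.5175 and 0.5350. OR = (0.5350/0.4650) / (0.5175/0.4825) = 1.073.
- v = 1% and 2%: OR = 1.012 and 1.024 by the same steps.

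The cohort size is not given. At an assumed 100,000 patients, the standard error of the log OR is about √(4/20,000 + 4/80,000) = 0.0158. Then z is about 2.2 and 4.4 for v = 3% and 6%, but 0.7 and 1.5 for v = 1% and 2%.

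**The case against.** The strongest defence is that the scope is deliberate. The two lists are separately labelled and consistent. The primary objective speaks of OAC treatment among NVAF patients, not of OAC prescribed because of AF, and an NVAF patient anticoagulated after VTE is not unprotected. A descriptive estimate may reasonably use a broader population than an outcome comparison. This stands to the extent that the difference is not a contradiction. It does not remove the need to justify the difference, or to show how much the results depend on it.

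The OAC-free requirement also weakens the size argument. Patients with earlier VTE and no OAC claim may be less likely than average to start OAC. The shift g × (q − p) changes sign when q falls below p, so even its direction is uncertain for part of the group. For transient AF, the codes are in an appendix that is not shown, so the make-up of that group cannot be checked.

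Three stronger readings are tempting but not supported:

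- **That the decision on objectives 2-5 is compromised.** Section 8.7 says "should the predictors/confounders from the primary objective be considered profound for the comparisons between the cohorts, objectives 2-5 will not be conducted", but this is a judgement about profound differences, alongside sample size. Odds ratios of the order shown above would hardly drive it. The two populations would differ even after the fix: 6-month post-index enrolment applies only to the primary population, and exclusions 3, 5 and 6 of Section 8.2.2.2 only to the secondary one.
- **That baseline utilization would absorb the effect.** Table 1 labels baseline costs and utilization as characteristics only, not as potential predictors.
- **That stepwise selection must retain spurious predictors.** This depends on the unknown cohort size and VTE share, and the protocol leaves the final list to clinical rationale as well.

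**Conclusion.** The point holds as a correctable weakness in the primary population. It does not invalidate the study. What the text establishes is the mismatch in exclusions, the indication-free definition of treatment, and the absence of any listed covariate or primary-objective analysis that deals with it.

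The size cannot be established from the documents. With a 50% treated share elsewhere, 1-6% VTE and 80-90% of those patients on OAC, the treated share is about 0.3 to 2.4 points too high. The lower end is more plausible the more patients the OAC-free requirement removes. Transient AF moves the share down if, as assumed, fewer of these patients receive OAC; with an OAC claim they count as ever-treated instead. Odds-ratio distortion is likely modest: 1.01 to 1.07 in the obesity example.

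**What to change.** Move exclusions 1, 2 and 4 of Section 8.2.2.2 (VTE, transient AF, hip/knee replacement within 6 weeks before index) to Section 8.2.1.2, so that they also apply to the primary objective and the high-risk subgroups, and align the Abstract. At minimum, pre-specify in Section 8.8 a primary-objective analysis with these exclusions, report the treated share and odds ratios both ways, and state why the populations differ.

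The criteria are already written and the protocol refers to its Appendix for the VTE and transient AF codes, so the work is small. The cost is a somewhat smaller cohort that no longer describes AF patients with concurrent VTE; reporting both ways avoids losing that description.

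These exclusions look back only to the index date, so OAC started for VTE or surgery arising later would still count as treatment. That should be stated as a limitation. Censoring such patients is not a good answer: the outcome is a binary status in a logistic model, and the rule would condition on events after index.
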